12.2.8. Pregnancy

If a participant becomes pregnant during the study, she must discontinue the study drug, but the investigator must follow up the pregnancy until the pregnancy outcome is available. Her obstetrician should be made aware of her study participation. The investigator should request information about the pregnancy outcome, including any possible fetal abnormalities and congenital defects. If a congenital abnormality or abortion (spontaneous) is reported, then it should be reported as an SAE.

Specific instructions for entry of these events will be provided in the eCRF Completion Guidelines.

12.3. Recording Adverse Events

12.3.1. Detection and Initial Report of Adverse Events

All participants will be monitored at the local study sites on a regular basis during the course of study involvement. Routine in-person and telephone follow-up visits offer the opportunity for PROMINENT study sites to ascertain any untoward medical events that might meet the criteria of an adverse event. Both in-person and telephone visits ask whether the participant has experienced any adverse events. All AEs are reported by completing an Adverse Event/Endpoint Form in the eCRF. A record of the type of AE, onset date, seriousness, severity (mild, moderate, or severe), and causality will be entered by the study site.

12.3.2. Trial Endpoints and Adverse Events

Primary endpoints are routinely assessed during in-person and telephone follow-up visits. Many of these clinical events will meet the criteria for SAEs. Endpoints will be reported by completing an Adverse Event/Endpoint Form in the eCRF.

12.3.3. Reporting Adverse Events

12.3.3.1. Investigator Responsibilities

Within 24 hours of receiving initial or additional information on SAEs, pregnancies, and special situations (ie, overdose, medication errors, off-label use, abuse, and suspected transmission of an infectious agent), the investigator should complete the relevant eCRF pages in the EDC system. Specific instructions for entry of these events will be provided in the eCRF Completion Guidelines.

The following minimum information must be reported:

- AE that meets the definition for serious
- Participant identification/randomization number

- Investigator/site number
- Study drug (pemafibrate vs. placebo)

In addition, the following information must be provided to the Sponsor with the initial report: 1) the date the investigator (or other site personnel) became aware of the event; and 2) the causality assessment.

Supporting source documents must be thoroughly blinded to protect the confidentiality of participants participating in the study before such documents are provided to the Sponsor or designated staff. Participant identifiers that should be redacted include but are not limited to participants' names, relatives' names, personal addresses, phone numbers, medical record, and accession numbers.

Once reported, automatic updates will be sent to the Sponsor and designated study staff. Initial reports will often not be complete. Central study staff will guide the site regarding the completion of an SAE form along with retrieval of the pertinent medical records for determination of a final diagnosis. Study site staff may contact participants directly to determine the resolution of AEs, if necessary.

In the event that the EDC is unavailable, and the 24-hour reporting timeline cannot be accommodated, such events will be reported by faxing the back-up paper SAE and/or pregnancy report form to Lifecycle Safety using the provided fax cover sheet and the appropriate fax number provided for your country. Once the EDC system becomes available, the investigator will enter SAEs reported on the paper SAE and/or pregnancy report form into the EDC system as soon as possible.

Additionally, sites must follow the requirements of their institutional IRB/IEC/REC for reporting AEs.

12.3.3.2. Sponsor Responsibilities

Reporting of SAEs will be done by the Sponsor (or designee) in accordance with their safety management plan and regulatory requirements.

The PROMINENT DSMB will review AEs that occur in the conduct of PROMINENT and may issue statements or guidance about the conduct of the study broadly or to individual sites. These statements will be reported by the Sponsor and sites as required. Refer to Section 12.4 for further details on the DSMB.

Additional SAE reporting for all participants will occur for central and/or local IRB/IEC/REC requirements, as relevant.

Primary endpoint events in this study will be waived from expedited reporting to health authorities, investigators, or IRBs/IECs/RECs; refer to Appendix B (Section 21.2) for a list of SMQ terms exempt from expedited reporting.

Medication errors, pregnancies and uses outside what is foreseen in the protocol, including misuse and abuse of the product, shall be subject to the same obligation to report as adverse events.

12.4. Data Safety Monitoring Board (DSMB)

Due to the potential risks to study participants, the size and multicenter nature of the study, and the fact that this is a Phase 3 clinical study, the study will have a formal and independent DSMB. The DSMB will be established by the EC and will include, at a minimum, members with specific expertise in the management of CVD and diabetes and familiarity with clinical study conduct, and a biostatistician with specific expertise in the design, analysis, and safety monitoring of multicenter clinical studies. The DSMB will operate under a charter agreed to by the Sponsor and will have the responsibility of monitoring outcome measurements/endpoints, AEs, and SAEs, and recommending termination of the study if it appears at any point during the study that the participants (or a subgroup of participants) are being placed at undue risk as a result of their participation.

The DSMB will meet (face-to-face or by teleconference) semi-annually to review accumulated data on safety and efficacy, and if appropriate, conduct an interim analysis of the data. Blinded data reports will be prepared by the data coordinating center (DCC) and un-blinded reports, if needed, will be prepared by the un-blinded DCC statistician prior to each meeting of the DSMB. Reports to the DSMB will include comparisons of baseline characteristics between treatment groups, displays of cumulative recruitment by study time, comparisons of post-randomization laboratory values by treatment group, and rates of AEs by treatment group, both overall and within system organ class (SOC). The DSMB will also receive summaries of lipid levels and concomitant lipid therapy dosing changes by treatment arm throughout the study to monitor imbalance in use of statins or other LDL-C lowering therapies. Summary statistics of safety laboratory testing will also be reviewed by the DSMB in important subgroups such as participants requiring CYP3A and CYP2C8 inhibitors. Based on DSMB review of blood safety data, effective from this global protocol amendment 2, the frequency of safety blood laboratory testing after Year 1 (Month 12) will be reduced to once annually, ie, the chemistry panel testing at intervening in-person visits will be discontinued.

Interim analyses of rates of the primary outcome, as well as rates of the individual components of the composite endpoint, and the prespecified secondary endpoints will also be prepared for presentation to the DSMB. The reports will be reviewed initially with DSMB members blinded to treatment group assignments. If, however, aggregate data suggests a trend toward harm in 1 treatment group, or at the request of the Sponsor's safety group, an un-blinded interim analysis may be requested and reviewed by the DSMB. Refer to Section 14.7 for further details.

Guidelines for the possible early termination of the study will be formulated by the DSMB, with a formal charter agreed upon prior to study enrollment. The proceedings of each meeting of the DSMB will be recorded in minutes. Any participant-specific protected health information reviewed by the DSMB will be kept completely confidential. Access to the closed session minutes of the DSMB meetings by Executive/Operations Committee (OC) Members, clinical site investigators, or members of the DCC, will be prohibited until after the database for the study has been locked and the study has been unblinded. A formal report will be submitted by the

Confidential K-877-302 Study Protocol

Version 3 dated 18-Mar-2020

DSMB to the EC, with a recommendation that the study be continued, modified in a manner to enhance participant safety, or terminated.

13. PATIENT REPORTED OUTCOMES

13.1. Quality of Life Assessment

Patient-reported quality of life assessments will be evaluated in this study using the following questionnaires:

• European Quality of Life – 5 Dimensions (EQ-5D-5L)

EQ-5D-5L will be completed at the Randomization Visit, annually thereafter, at the first in-person visit after a primary or secondary endpoint occurs, and at the CSED Visit. The data collected may be used in pharmacoeconomics assessment.

14. STATISTICS

14.1. Stratification and Randomization

Participants willing and eligible to be randomized will be stratified by the following: sex, prior history of CVD (primary vs. secondary prevention cohorts), and statin use at baseline, defined as those who are taking no statin at baseline or are statin intolerant compared to all others. Within each strata, participants will be randomized with equal probability to active K-877 or placebo.

14.2. Sample Size and Power

The study was designed using an event-driven approach where all participants are followed until a sufficient number of events have accrued. Regardless of the rate of major CV events in the placebo group, the study must accrue 1279 adjudicated and confirmed major CV events (with a minimum of 200 events accrued in women) in order to have 90% power to detect a 16.6% reduction in the rate with pemafibrate, based on a 2-sided test with alpha = 0.05. The sample size has been increased by 1.9% to maintain 90% power in the presence of interim monitoring. Consequently, we stipulate that the study will require accrual of 1,304 total primary events as reported in Table 6.

Using the approach of Lachin and Foulkes under the assumption of a uniform hazard we can estimate the duration of the study.⁶⁴ We will use the following assumptions:

- 1. The **recruitment will be uniform over a 30-month period**. Each randomized participant will be asked to continue blinded treatment until the study completion (when sufficient endpoints have been accrued).
- 2. Unless otherwise specified, power is set at 90% to detect the specified effect.
- 3. As these participants have strong affiliations with their treatment centers and will have been tested in a Placebo Run-In Period, low rates of loss to follow-up are anticipated. Power calculations assume a 1% annual loss to follow-up.
- 4. Sample size is assumed to be **10,000 randomized participants** (5000 receiving pemafibrate and 5000 receiving placebo).

Based on previous studies, it is anticipated that **annual event rates will be between 3.5 and 4.5 per 100 person-years** in the placebo group. We expect a higher event rate in the secondary prevention cohort (~2/3 with prior CVD) than the primary prevention cohort (~1/3 with no prior CVD). For example, a total annual event rate in the placebo group of 4.5 per 100 person-years could be achieved via an event rate of 5.2 per 100 person-years in the secondary prevention group and 3 per 100 person-years in the primary prevention group.

Under these assumptions, Lachin and Foulkes show that the power of the study with N total randomized participants in the pemafibrate and placebo groups combined is:

$$Power = \Phi^{-1}\left(\frac{\sqrt{N}|\lambda_e - \lambda_c| - Z_\alpha \sqrt{\Psi(\bar{\lambda})(Q_e^{-1} + Q_c^{-1})}}{\sqrt{2\Psi(\lambda_e) + 2\Psi(\lambda_c)}}\right)$$

where Φ is the standard normal distribution function, and $\psi(\lambda)$ is defined as follows:

$$\Psi(\lambda) = \lambda^{2} \left\{ \frac{\lambda}{(\eta + \lambda)} \left[1 - \frac{\left[e^{\left(- (T_{f} - T_{r})(\eta + \lambda)} \right)} - e^{\left(- T_{f}(\eta + \lambda) \right)} \right] \right\}^{-1} \\ = \lambda(\lambda + \eta) / \left(1 - \frac{\left[exp\left(- (T_{f} - T_{r})(\lambda + \eta) \right) - exp\left(- T_{f}(\lambda + \eta) \right) \right]}{T_{r}(\lambda + \eta)} \right)$$

λ_e is the incidence rate in the pemafibrate group,

 Q_e is the proportion of the total participants in the pemafibrate group,

 λ_c is the incidence rate in the placebo group,

 Q_c is the proportion of the total participants in the placebo group,

 η is the loss to follow up rate,

 T_r is the recruitment duration,

T_f is the follow-up duration (also equal to the length of the study,

 Z_{α} is the standard normal deviate at level α , and

$$\bar{\lambda} = Q_e \lambda_e + Q_c \lambda_c = .5\lambda_e + .5\lambda_c$$

These power calculations are based on the Intent-to-Treat (ITT) population analyses. The actual duration of enrollment (3.0 years) was updated for assumptions. In our power calculations, we used a range of pemafibrate non-compliance from 10% (at time of enrollment closure) up to a conservative 17%, and also assumed that none of the placebo group will initiate pemafibrate therapy (drop-in). The impact of noncompliance on power can be evaluated from interpolation using Table 6. For example, if the true rate of major CV events in persons meeting eligibility criteria but not on pemafibrate is 4.5 per 100-person years, and fully compliant pemafibrate reduces this rate by 20%, we estimate a rate of the primary endpoint of 3.8 per 100 person-years in the pemafibrate group and 4.5 per 100 person-years in the placebo group allowing for a conservative pemafibrate non-compliance of 17%, using 3 year enrollment period, and 1% annual loss to follow-up. This would correspond to an observed 16.6% reduction in the active treatment group relative to placebo with the above noncompliance and drop-in rates. The proposed study would thus require about 5 years of follow-up (from first patient randomized to study termination) to have power above 90% to detect the anticipated effect on observed event rates and ITT analyses, as summarized in Table 6.

With respect to the above assumptions on accrual and drop out, and the range of event rates in the placebo group shown in Table 6, the proposed study with 10,000 randomized participants would be expected to require approximately 5 years of follow-up (approximate placebo event rate=4.5/100 person-years) under the assumption of a 16.6% reduction in hazard associated with pemafibrate.

Table 6: Number of Primary Endpoints and Estimated Study Duration in Years to Achieve 90% Power with 10,000 Randomized Participants

Pemafibrate Non-	Relative Rate	Events (adjusted for	Rate of Major Cardiovascular Events in the Placebo Group (per 100 person-years)		
Compliance		Monitoring)	3.5	4.0	4.5
17%	0.834	1304	5.9 years	5.3 years	4.9 years
15%	0.830	1238	5.6 years	5.1 years	4.7 years
10%	0.820	1092	5.1 years	4.7 years	4.3 years

14.3. Demographics and Baseline Characteristics

The randomized design and large sample size of 10,000 should provide a balanced distribution of demographic and baseline characteristics between the 2 treatment groups. Nonetheless, initial analyses will be conducted to identify any chance imbalances in the distribution of these characteristics. In particular, these analyses will form part of the routine monitoring of the study and will be regularly reported to the DSMB. For continuous and ordinal variables, including age and baseline levels of risk factors including lipid levels, blood pressure, BMI, duration of diabetes, and baseline HbA1c, comparisons between treatment groups will be made using the Wilcoxon rank-sum test. For categorical variables, including sex, race, current and former cigarette smoking, past history of CVD, congestive heart failure (CHF), atrial fibrillation, peripheral vascular disease, hypertension, and concomitant therapies, comparisons between treatment groups will be made using Chi-square tests. These hypothesis tests are intended for data monitoring and quality control, and not to determine which baseline covariates to include in efficacy analyses.

14.4. Primary Analyses

The primary endpoint of the study is the time from randomization to the first occurrence of any component of the clinical composite endpoint of nonfatal MI, nonfatal ischemic stroke, coronary revascularization, or CV death. The primary analysis of the study will use a likelihood ratio test based on a proportional hazards model stratified on sex, prior history of CVD (primary vs. secondary prevention cohorts), and statin use at baseline, defined as those who are taking no statin at baseline or are statin intolerant compared to all others, to test the null hypothesis of no association between assignment to pemafibrate and the rate of the primary endpoint.

The ITT population will serve as the primary analysis population and will include all randomized participants who received at least 1 dose of study treatment. Participants will be analyzed according to their randomized treatment group, regardless of whether they adhere to their assigned treatment. Statistical significance will be based on a 2-sided test with level 0.05. The estimated relative hazard in the pemafibrate group compared to the placebo group with an accompanying 95% CI will quantify the treatment effect. If this relative hazard is less than 1, then 100*(1-estimated relative hazard) will be defined as the percent reduction in hazard associated with pemafibrate treatment.

Rates of occurrence of the primary endpoint will be defined as the total number of participants who have this event in a treatment group per 100 person-years of follow-up, counting all time from randomization until the first of the event, death, end of trial, or withdrawal of consent, whichever comes first. Estimates of the probability of the primary endpoint by time after randomization within treatment groups will be based on the method of Kaplan and Meier. 66 We will also use the proportional hazards model to control for baseline factors that might influence the rate of the primary endpoint (eg, age, race, sex, baseline comorbidities, and concomitant medications), as control for these variables may yield more efficient estimates of relative treatment effects. 67 If Kaplan-Meier plots of event-free survival by study time, or related plots of log(-log)(survival), indicate violations of the proportional hazards assumption, or a formal test of trend in the scaled Schoenfeld residuals indicates such a violation, then weighted log-rank tests will be used according to strategies described by Pecková and Fleming.⁶⁸ However, even in the presence of an apparent violation of the proportional hazards assumption, the primary analysis described above gives a valid (although perhaps not optimal) test of the main study hypothesis and will remain the primary analytic strategy, with these weighted log-rank tests serving as sensitivity analyses.

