- Worsening ischemic discomfort (rest angina, or severe angina (Canadian Cardiovascular Society (CCS) classification severity ≥ Class III) new in onset (<2 months) or increasing angina intensity, duration, and/or frequency, with an increase in severity of at least 1 CCS class to at least CCS III)
- Unscheduled hospitalization
- No elevation in cardiac biomarkers
- An attempt (even if unsuccessful) at percutaneous or surgical coronary revascularization during the index hospitalization, or after a transfer to another institution that then performs those procedures, provided that there is no interceding home discharge

Definitions of Cardiovascular, Non-Cardiovascular, and Undetermined Cases of Death

The classifications for death are drawn from Hicks et al. ⁶² Death is classified into 1 of 3 categories: CV, non-CV, or undetermined cause of death. The intent is to identify 1 of these categories as the underlying cause of death. The key priority is differentiating between CV and non-CV causes of death. Death attribution can be difficult, particularly for sudden death, even when witnessed. Sudden deaths are usually attributed to sudden cardiac death (CV death) or death due to an undetermined cause. The underlying cause of death (the attributable cause of death) and the most proximate event associated with death may overlap substantially. Generally, the attributable cause of death is preferred.

Cardiovascular death can be due to: acute MI; sudden cardiac death; HF; stroke; a CV procedure; CV hemorrhage; or other CV cause.

Cardiovascular death due to acute MI: Death by any CV mechanism (eg, arrhythmia, sudden death, HF, stroke, pulmonary embolus, PAD) within 30 days after an acute MI, related to the immediate consequences of the MI, such as progressive HF or recalcitrant arrhythmia. There may be assessable (attributable) mechanisms of CV death during this time period, but for simplicity, if the CV death occurs within 30 days of an acute MI, it will be considered a death due to MI.

Note: Acute MI should be verified to the extent possible by the diagnostic criteria outlined for acute MI or by autopsy findings showing recent MI or recent coronary thrombosis. Death resulting from a procedure to treat an MI (PCI or CABG), or to treat a complication resulting from MI, should also be considered death due to acute MI. Death resulting from an elective coronary procedure to treat myocardial ischemia (ie, chronic stable angina) or death due to an MI

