To assess the effect of non-informative censoring on the primary outcome, analyses will be performed following the reference-based method outlined by Carpenter, Roger, and Kenward⁶⁹ and detailed in the Statistical Analysis Plan using the piece-wise exponential method described by Lipkovich at al.⁷⁰ For those participants who were lost-to-follow-up, event status after the time of last observation is imputed using the distribution of retrieved dropouts for each arm. Retrieved dropouts are defined as participants who are no longer taking study drug but have agreed to continue to be followed. Other imputation models for missing data will also be explored for their effect on the primary outcome, including models that use the entire placebo group as the reference.

Separate proportional hazards models will also be used to compare the effects of pemafibrate treatment on time to each of the individual components of the composite primary endpoint. Analyses will use methods of competing risks survival analysis and compare the relative effects of randomized treatments on the different components of the composite outcome.^{72, 73} The approach of Lunn and McNeil⁷² provides a readily accessible implementation of a classical approach to competing risk analysis developed by Kalbfleisch and Prentice.⁷⁴

Secondary lipid efficacy endpoints will be analyzed using analysis of covariance (ANCOVA) with a retrieved dropout-based pattern mixture model. Participants with missing data will be imputed using the distribution of retrieved dropouts for each arm, where retrieved dropouts are defined as participants who are no longer taking study drug but have agreed to continue to be followed. Imputed data will be analyzed using an ANCOVA model with baseline measurement as a covariate and the treatment arm and randomization strata as fixed effects.

While all primary analyses are on the ITT population, a Per-Protocol population will also be analyzed which will be limited to participants with no major protocol deviations. Sensitivity analyses for the primary efficacy endpoint will also be conducted examining the effect of compliance and escalation of other lipid-lowering medications. Longitudinal analyses will quantify the impact of pemafibrate on lipid levels, biomarkers of inflammation, and glycemic parameters and other prespecified exploratory lipid and non-lipid biomarkers (Tertiary Endpoints: Section 5.3.1).

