8. EFFICACY

8.1. General Considerations

The following will be applied to all efficacy analyses where applicable.

The ITT population will be used in the analysis of efficacy endpoints. Endpoints will be summarized by treatment group unless otherwise stated. Results will be presented by region and center where appropriate. Extreme results by region or center will be noted.

The summary statistics for the efficacy endpoints and their individual components will be provided. These statistics include the number of first events (i.e. the number of subjects with the event), the total exposure to first event or censoring time, the annualized event rate, and the Kaplan Meier estimates, when applicable. The annualized event rate will be calculated as the number of subject with events divided by the total time at risk (years) to the subjects' first event or censoring time. The hazard ratio of the exposure group versus placebo with 95% CIs will be provided using the Cox proportional hazards model including treatment. The model will be stratified by the three stratification variables, sex, prior history of CVD, and baseline statin use, under the assumption of differing baseline hazards.

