8.4. Analysis of the Primary Efficacy Endpoint

8.4.1. Primary Efficacy Analysis

The primary endpoint of the trial is the time from randomization to the first occurrence of any component of the clinical composite endpoint of nonfatal myocardial infarction, nonfatal ischemic stroke, cardiovascular death, and coronary revascularization.

Patients who do not have an event will be censored at withdrawal of consent, end of study, or death. The censor date will be the date of withdrawal of consent for follow-up, CSED or the subject's last assessment, or death, whichever comes first. The time to event/censoring in days will be derived as (Date of First Occurrence of Event/Censoring – Date of First Dose) +1. The primary analysis of the trial will use a likelihood ratio test based on a proportional hazards model stratified on sex, prior history of CVD, and statin use at baseline to test the null hypothesis of no association between assignment to active K-877 and the rate of the primary endpoint. All analyses will classify patients according to their randomized treatment assignment, i.e. according to the intention to treat principle, and will base evaluation of statistical significance on a two-sided test with level 0.05. The estimated relative hazard in the K-877 group compared to the placebo group with an accompanying 95% confidence interval will quantify the treatment effect. If this relative hazard is less than 1, then 100*(1-estimated relative hazard) will be defined as the percent reduction in hazard associated with K-877 treatment. Rates of occurrence of the primary endpoint will be defined as the total number of subjects who have this event in a treatment group per 100 person-years of follow-up. Estimates of the probability of the primary

```
Kowa Research Institute, Inc.
Statistical Analysis Plan – Protocol K-877-302 (PROMINENT)
```

endpoint by time after randomization within treatment groups will be based on the method of Kaplan and Meier.

Analysis will be implemented using the SAS® procedure PHREG as follows:

```
PROC PHREG DATA = ...;

CLASS TREATMENT (ref='2');

MODEL AVAL*CNSR(1) = TREATMENT;

STRATA SEX CVD STATIN;

HAZARDRATIO TREATMENT / ALPHA=0.05;

RUN;

where AVAL = time to event

TREATMENT = Randomized treatment group (pemafibrate and placebo)

CNSR = Censoring variable - 0 = Event, 1 = Censored

SEX = sex

CVD = prior history of CVD

STATIN = statin use at baseline
```

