The total events analysis (second part of endpoint 6) will use negative binomial regression, with outcome being the total number of such events, a log link function, and a subject's total follow-up time as an offset. The independent variable will be randomized treatment assignment, and the

```
Kowa Research Institute, Inc.
Statistical Analysis Plan – Protocol K-877-302 (PROMINENT)
```

model will consider the following variables as fixed effects: sex, prior history of CVD, and statin use at baseline.

The analysis of heterogeneity of treatment effect by PPAR- α genetic polymorphisms will use a Cox proportional hazards model including two stratification variables: sex and prior history of CVD. This is due to both the low level of statin intolerance at baseline and concern that some of the genetic subgroups may be sparse.

In addition to the separate analyses of each component of the primary endpoint, possible heterogeneity in their effects across components will be evaluated. Analyses will use methods of competing risks survival analysis and compare the relative effects of randomized treatments on the different components of the composite outcome^{4, 5}. The approach of Fine and Gray provides a readily accessible implementation of a classical approach to competing risk analysis developed by Kalbfleisch and Prentice⁶.

In addition to the individual components of the composite primary endpoint, other CVD endpoints will be evaluated for treatment effect, including time to all-cause mortality, time to first MI, time to first stroke, time to first ischemic stroke, and time to first hemorrhagic stroke. Analyses will consider both fatal and non-fatal events where appropriate.

Secondary Group B lipid efficacy endpoints will be analyzed using analysis of covariance (ANCOVA) with a retrieved dropout based pattern mixture model. Subjects with missing data will be imputed using the distribution of retrieved dropouts for each arm, where retrieved dropouts are defined as participants who are no longer taking study drug but have agreed to continue to be followed. Imputed data will be analyzed using an ANCOVA model with baseline measurement as a covariate and the treatment arm and randomization strata as fixed effects.

Analysis using an ANCOVA model will be implemented using the SAS® procedure MIXED as follows:

```
PROC MIXED DATA = ...;

CLASS TREATMENT SEX CVD STATIN;

MODEL PCHG = BASELINE TREATMENT SEX CVD STATIN;

LSMEANS TREATMENT / DIFF CL;

RUN;

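### Kaplan-Meier with non-cardiovascular deaths censored modestly overstates the probability of the primary endpoint in each arm

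*Protocol*

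**What the plan says.** Protocol 14.4 describes the absolute risk estimate for the composite as follows: "Estimates of the probability of the primary endpoint by time after randomization within treatment groups will be based on the method of Kaplan and Meier". SAP 8.4.1 says the same.

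Both documents end follow-up at death from any cause. For the event rates, Protocol 14.4 counts time from randomization "until the first of the event, death, end of trial, or withdrawal of consent, whichever comes first". SAP 8.4.1 states the censoring rule directly: "Patients who do not have an event will be censored at withdrawal of consent, end of study, or death".

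The composite includes cardiovascular death and no other death. Protocol 11.1 sorts deaths into three groups: "Death is classified into 1 of 3 categories: CV, non-CV, or undetermined cause of death". I found no rule in either document that counts undetermined deaths as cardiovascular, so these appear to be censored along with non-cardiovascular deaths.

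For components, SAP 8.1 says "The summary statistics for the efficacy endpoints and their individual components will be provided", and its list of statistics includes "the annualized event rate, and the Kaplan Meier estimates, when applicable". It does not say when Kaplan-Meier would not apply.

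Competing-risks methods are planned elsewhere. Protocol 14.5 says "Analyses will use methods of competing risks survival analysis and compare the relative effects of randomized treatments on the different components of the composite outcome". SAP 8.5 keeps that aim and names a method: "The approach of Fine and Gray provides a readily accessible implementation of a classical approach to competing risk analysis".

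**The concern.** A participant who has died of cancer or infection cannot go on to have the primary endpoint. Kaplan-Meier treats that participant as censored and in effect assigns the future risk of those still alive. One minus Kaplan-Meier then answers a hypothetical question, namely what the risk would be if deaths outside the endpoint did not happen. It does not give the probability that a randomized participant has the endpoint by a given time, which is the quantity the text names. The error always runs upward, and it grows with follow-up time and with the rate of competing death.

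Nothing else in the plan corrects it. SAP 6.7.1 assumes non-informative censoring for the main time-to-event analyses and makes no exception for death. The reference-based imputation in Protocol 14.5 is for participants lost to follow-up. The competing-risks analyses compare relative effects across components, and neither document specifies a cumulative incidence estimate of absolute risk.

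What is at stake is the accuracy of the reported arm-specific probabilities. For a nonfatal component every death competes, so a Kaplan-Meier figure reported there has the same problem.

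**Working it through.** **Inputs from the documents.** Placebo rate 4.5 per 100 person-years and hazard ratio 0.834 (Protocol 14.2). The implied pemafibrate rate is 4.5 × 0.834 = 3.753, which matches the 3.8 stated there. Study length is about 5 years with a 3.5-year average follow-up (Protocol synopsis, sample size justification). The plan states no Kaplan-Meier risk, so there is no such figure to reproduce.

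**Assumptions.** Hazards are constant. Non-cardiovascular death is set at 0.5 to 2.0 per 100 person-years, because the documents give no rate. Component and all-cause death rates are also assumed below.

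**Formulas.** With endpoint hazard λ and competing death hazard μ:

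- One minus Kaplan-Meier = 1 − exp(−λt)
- Cumulative incidence = λ/(λ+μ) × [1 − exp(−(λ+μ)t)]

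**Composite at 5 years.** Placebo Kaplan-Meier: 1 − exp(−0.045 × 5) = 20.15%. Pemafibrate: 1 − exp(−0.03753 × 5) = 17.11%. Difference: 3.04 points. Cumulative incidence for placebo at μ = 0.005 is 0.045/0.050 × [1 − exp(−0.25)] = 19.91%, and at μ = 0.02 it is 0.045/0.065 × [1 − exp(−0.325)] = 19.21%. The full set, with equal μ in both arms:

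| Assumed non-CV death per 100 PY | Placebo incidence | KM excess (points) | Pemafibrate incidence | KM excess (points) | Risk difference (points) |
|---|---|---|---|---|---|
| 0.5 | 19.91% | 0.24 | 16.90% | 0.21 | 3.00 |
| 1.0 | 19.67% | 0.48 | 16.70% | 0.41 | 2.97 |
| 1.5 | 19.44% | 0.71 | 16.50% | 0.61 | 2.94 |
| 2.0 | 19.21% | 0.94 | 16.31% | 0.80 | 2.90 |

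The placebo excess is 1.2% to 4.9% in relative terms. The risk difference falls from 3.04 by between 0.04 and 0.14 points.

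**Composite at 3.5 years, placebo.** Kaplan-Meier gives 14.57%, against 14.45% (μ = 0.005) to 14.09% (μ = 0.02), an excess of 0.12 to 0.49 points.

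**Unequal competing death, 5 years.** With 1.5 on placebo and 1.0 on pemafibrate (assumed), the difference in cumulative incidence is 19.44 − 16.70 = 2.74 points. With the rates reversed it is 19.67 − 16.50 = 3.17. Kaplan-Meier gives 3.04 in both cases.

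**Nonfatal component, 5 years.** At an assumed 1 per 100 person-years with all-cause death at 2 to 3, Kaplan-Meier gives 4.88%, against 4.64% to 4.53%. That is 0.23 to 0.35 points, or 5% to 8% relative. With non-cardiovascular death at 1.0 and cardiovascular death at 1.0, the excess in points is 0.23 for a component rate of 1.0 and 0.56 for a rate of 2.5, against 0.48 for the composite.

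**The case against.** The strongest reply is that this is a descriptive curve on which little depends. The treatment effect is quantified by the hazard ratio and its confidence interval. The other planned absolute measure, events per 100 person-years, stops the clock at death and does not have this problem. Neither document plans a risk difference, a number needed to treat or a benefit-risk calculation from these curves. A reader might infer that the trial's absolute risk reduction will be biased, but the plan does not define one. If one were formed with equal non-cardiovascular death in the arms, a shift of 0.04 to 0.14 points would be small beside sampling error. With 5,000 per arm and complete follow-up, the 95% half-width of the 5-year difference is 1.96 × √[(0.2015 × 0.7985 + 0.1711 × 0.8289)/5000], or about 1.5 points. Even the largest single-arm excess (0.94) is below its own half-width of about 1.1.

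All of that stands, and it limits the point to a modest one. It does not make the named probability correct. The excess is systematic, and a larger sample does not remove it. The plan also cannot know in advance that non-cardiovascular death will match between arms.

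Two other replies stand in part. First, SAP 8.1 qualifies Kaplan-Meier for components with a condition, so its use there is likely but not certain. Second, competing-risks methods are planned for the components, so it would be wrong to say that the plan ignores competing risks. Their stated purpose, however, is relative effects. The Group A endpoint that adds all-cause mortality has no competing death, but it is a different endpoint.

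**Conclusion.** The point holds in a limited form. As written, the plan overstates the probability of the primary endpoint in each arm. The direction is certain whenever deaths outside the endpoint occur. The size rests on assumed death rates and constant hazards: 0.2 to 0.9 points at 5 years and about 0.1 to 0.5 points at 3.5 years for the placebo arm. The between-arm difference barely moves unless non-cardiovascular death differs by arm.

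Two stronger readings are not supported. The primary likelihood ratio test and hazard ratio are not biased by this choice, since censoring other deaths is the normal way to estimate the cause-specific hazard ratio. And the overstatement is not generally worse for nonfatal components: it is larger in relative terms (about 5% to 8% under the assumed rates), but in percentage points it can be smaller or larger than for the composite, depending on the component's rate. The change is worth making because it corrects a mislabelled quantity at almost no cost.

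**What to change.** In Protocol 14.4 and SAP 8.1 and 8.4.1, report the probability of the primary endpoint by arm as Aalen-Johansen cumulative incidence. Competing events should be non-cardiovascular deaths together with deaths of undetermined cause that are not counted in the endpoint. The text should say explicitly how undetermined deaths are handled. Where absolute risks of components are reported, treat every death not counted in that component as competing.

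Keep the Kaplan-Meier and log(-log) survival plots, because Protocol 14.4 relies on them to check proportional hazards. Keep Kaplan-Meier as the estimate for the endpoint that includes all-cause mortality. Leave the stratified Cox model and its test unchanged.

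The cost is one extra standard output and slightly lower reported absolute risks. Deaths are already classified by cause under Protocol 11.1, so no new data are needed.
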